4.1.4 Exploratory Endpoints

Any comparisons across timepoints (baseline to 6 months) not described in the primary or secondary endpoints, including but not limited to:

- Demographics
- Medical History
- History of joint osteoarthritis
- Injection procedure
- Concomitant medications
- Non-drug therapy

For the exploratory analyses, the continuous variables will be summarized via descriptive statistics (n, mean, median, standard deviation, minimum, and maximum. The discrete variables will be summarized via counts and percents.

4.2 STATISTICAL METHODS

Tabulation of summary statistics, graphical presentations, and statistical analyses will be performed using SAS[®] software 9.4 or higher version. Where not otherwise specified, the last pre-treatment observation will be used as baseline for calculating post-treatment changes from baseline. The primary presentations and analyses will be based on data pooled across study centers.

Relevant summaries for individual centers, or combinations of centers, may be presented for primary data. All testing and confidence intervals will use a significance level of 5%.

4.3 DEMOGRAPHIC AND BASELINE CHARACTERISTICS

All demographic and baseline characteristics will be tabulated by treatment group and a test of homogeneity between the treatment groups will be conducted. For continuous variables (e.g. age, height, weight) a one way ANOVA will be used. For categorical variables (e.g. gender, race), a Fisher's exact test or chi-squared test will be used. Medical history findings, physical examinations and concomitant medications will be tabulated by treatment group.

The baseline, Vital Signs, and BMI data will be summarized via descriptive statistics and tested for homogeneity using a one way ANOVA.

4.4 ADVERSE EVENTS

All AEs will be coded according to MedDRA. Safety assessments will include Treatment-Emergent Adverse Events (TEAEs) which are defined as AEs with an Investigator assessment of definitely, probably, or possibly related to CTM. TEAEs will be summarized with frequencies and percentages by system organ class and preferred term, severity, and relationship to study CTM for each treatment group. In summaries of TEAEs by severity and relationship to CTM for subjects reporting multiple episodes, all reported events will be included, not only the worst reported case. Serious Adverse Events will also be presented by relationship to the CTM.

The number of subjects with at least one AE will be tabulated for each treatment group. Differences between the treatment groups will be tested using Fisher's exact test. Then the number of AEs for each treatment group will also be tabulated.

The number of subjects and the number of AEs will be tabulated by severity, relationship, and local injection site specific events versus non local events.

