6.3 Exploratory Endpoints

Any comparisons across timepoints (baseline to 6 months) not described in the primary or secondary endpoints, including but not limited to:

- Demographics
- Medical History
- History of joint osteoarthritis
- Rescue Medication Use
- Treatment Failure
- Injection procedure
- Concomitant medications
- Non-drug therapy.

6.4 Safety Endpoint:

The incidence, severity, and relationship to treatment of all Adverse Events (AE) will be collected from the treatment injection to the 6-month assessment.

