9.2.2 Adverse Events

Subjects with AEs will be summarized with frequencies and percentages by system organ class and preferred term, severity, and relationship to investigational product/procedure. In summaries of AEs by severity and relationship to investigational product/procedure, subjects reporting multiple episodes will be counted once under the worst severity and the strongest relationship, respectively. Serious Adverse Events will also be presented by relationship to investigational product/procedure.

Adverse events occurring prior to the index treatment will not be recorded in this trial.

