3.0 Objectives

The goal of these studies is to demonstrate the clinical improvement and safety in patients treated with CINGAL for hip osteoarthritis, shoulder osteoarthritis, and ankle osteoarthritis. Specifically, this study will provide confirmation to the effectiveness and safety of CINGAL at relieving the specified joint pain to 6 months post-treatment.

PRIMARY ENDPOINT:

• Reduction of index joint Numerical Rating Scale (NRS) pain on walking from baseline to 6 Months post injection (CINGAL 20-01), joint pain from baseline to 6 Months post injection (CINGAL 20-02), and pain on walking from baseline to 6 Months post injection (CINGAL 20-01).

SECONDARY ENDPOINTS:

- Improvement in Lequesne Hip index joint from baseline to 6 months post injection. (CINGAL 20-01 only)
- Improvement in DASH score for index joint from baseline to 6 months post injection (CINGAL 20-02 only)

- Improvement in AOFAS index joint from baseline to 6 months post injection (CINGAL 20-03 only).
- Improvement in Patient Global Assessment (PGA) from baseline to 6 months post injection.
- OMERACT-OARSI responder rate in the index joint at 6 months post injection.
- Time to treatment failure
- Reduction in Medication usage from baseline to 6 months post injection.

EXPLORATORY ENDPOINTS

Any comparisons across timepoints (baseline to 6 months) not described in the primary or secondary endpoints, including but not limited to:

- Demographics
- Medical History
- History of joint osteoarthritis
- Rescue Medication Use
- Treatment Failure
- Injection procedure
- Concomitant medications
- Non-drug therapy

SAFETY ENDPOINT:

The incidence, severity, and relationship to treatment of all Adverse Events (AE) will be collected from the treatment injection to the 6 month assessment.

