4.5 SUBJECT POPULATIONS

All safety analyses will be conducted on all subjects who undergo treatment in any group.

The Safety Population will be defined as all subjects who undergo at least one Study Treatment, and the safety analysis will be performed on this population.

The primary analysis on the primary endpoint will be performed on the Intent to Treat (ITT) population, defined as all patients who were treated in the study. All Primary and Secondary endpoints will be analyzed using the ITT population.

A secondary analysis will be conducted on the Per Protocol (PP) population. Since the primary endpoint is at 6 Months, this is all subjects who complete the 6 Month visit and who do not have a major deviation from the protocol. For all other assessments, this is defined as the subjects who complete those assessments according to the protocol.

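### SAP 4.4 limits the coded adverse event tables to events judged related to CTM and counts every episode, where protocol 9.2.2 tabulates all AEs and counts each subject once

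*SAP*

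**What the plan says.** **Which events are coded and tabulated.** SAP 4.4 has all AEs coded in MedDRA, then defines TEAEs as those "which are defined as AEs with an Investigator assessment of definitely, probably, or possibly related to CTM". The coded display follows from that definition: "TEAEs will be summarized with frequencies and percentages by system organ class and preferred term". Protocol 9.2.2 sets no relatedness condition: "Subjects with AEs will be summarized with frequencies and percentages by system organ class and preferred term, severity, and relationship to investigational product/procedure". The safety endpoint is worded for all AEs in both documents; SAP 3.0 reads "The incidence, severity, and relationship to treatment of all Adverse Events (AE) will be collected from the treatment injection to the 6 month assessment", and protocol 6.4 is the same in substance.

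**How repeated episodes are counted.** In summaries by severity and relationship, protocol 9.2.2 says "subjects reporting multiple episodes will be counted once under the worst severity and the strongest relationship, respectively". For the TEAE summaries, SAP 4.4 says "all reported events will be included, not only the worst reported case".

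**What else the SAP plans for all AEs.** SAP 4.4 tabulates subjects with at least one AE, the number of AEs, and both subjects and AEs by severity, relationship and local versus non-local. None of these is broken down by system organ class or preferred term. SAP 1.0 mentions data listings, but no AE listing is described. SAP 4.5 defines the Safety Population as the treated subjects and adds that "the safety analysis will be performed on this population".

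**The concern.** A treatment-emergent event is normally identified by when it starts, with causality reported as a separate attribute. SAP 4.4 merges the two, so its TEAE tables are in fact tables of related AEs under another name.

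Safety is one of the study's two stated goals, and the joint is new for this product. The study is open-label with a single arm, so an unblinded causality judgement would decide which types of event appear in the coded tables at all. A cluster of one event type that investigators consider unrelated would add to the overall AE count, but no planned table would show what it was.

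The counting difference leaves two prespecified answers for the same severity and relationship figures. The SAP neither mentions nor explains the change from the protocol.

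**Working it through.** Neither document states a figure to reproduce. The check is a comparison of text, followed by hypothetical counts to show size.

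**Step 1: scope of the coded tables.** In SAP 4.4, system organ class and preferred term are named once, for TEAEs. No other SAP section plans a coded AE table.

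| Display | Protocol 9.2.2 | SAP 4.4 |
|---|---|---|
| System organ class / preferred term | all subjects with AEs | related to CTM only |
| Severity and relationship, repeated episodes | subject once, worst / strongest | every episode (TEAEs) |
| SAEs by relationship | product/procedure | CTM |
| Uncoded counts of all AEs | – | subjects and events, by severity, relationship, local/non-local |

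The uncoded all-AE row does not restore the protocol's counting rule. It counts subjects and events but does not say whether a subject with several episodes appears once or in each category.

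**Step 2: size of the coding gap.** Inputs: N = 25 (planned enrollment in both documents) over the Safety Population; the AE counts are assumed. Suppose a preferred term occurs in 3 subjects, and in k of them the event is judged related to CTM.

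- Protocol: 3/25 = 12%, whatever k is.
- SAP: k/25, which is 0/25 = 0%, 1/25 = 4%, 2/25 = 8% or 3/25 = 12% for k = 0, 1, 2, 3.

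With k = 0 the term does not appear in the coded table.

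**Step 3: size of the counting difference.** Assume every event is related to CTM, so that all are TEAEs and only the counting rule matters. Nine subjects have one mild AE each; a tenth has three mild and one severe. That is 9 + 4 = 13 events in 10 subjects, of which 12 are mild and 1 is severe.

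| Rule | Mild | Severe | Sum of rows |
|---|---|---|---|
| Protocol, worst severity per subject | 9/25 = 36% | 1/25 = 4% | 10/25 = 40% |
| SAP, subject counted in each category | 10/25 = 40% | 1/25 = 4% | 11/25 = 44% |
| SAP, events over 25 | 12/25 = 48% | 1/25 = 4% | 13/25 = 52% |

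Only the protocol's rule gives rows that add to the proportion of subjects with any AE, 10/25 = 40%. The SAP does not say which of its two readings is meant.

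**Step 4: related points.**

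- CTM is not defined in the text available. If it means the product alone, events attributed only to the injection procedure, which protocol 8.3 rates separately, also leave the coded tables, and the SAE presentation narrows from product/procedure to product.
- The SAP's three relationship terms are not mapped to the five levels in protocol 8.3, which include no definite level. The CRF may use other terms.
- Protocol 8.2 starts AE recording at enrollment; 6.4, 8 and 9.2.2 start it at injection. If recording starts at injection, an onset-based TEAE definition keeps essentially every recorded AE. If it starts at enrollment, an onset criterion is needed to separate pre-injection events, and the SAP has none.

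**The case against.** The strongest reply is that little is lost:

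- The endpoint asks for incidence, severity and relationship of all AEs, and SAP 4.4 plans uncoded counts of exactly those.
- The endpoint itself does not call for coded terms.
- The sentence introducing TEAEs is not exclusive, SAP 4.1 presents itself as detailing the protocol's analysis, and every AE is coded. The missing table could therefore be produced without breaching the SAP, and with 25 subjects the practical effect is limited.

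This stands as far as it goes: the gap is an omission, not a prohibition, and it concerns the coded breakdown rather than all AE reporting. But a table that could be added is not a planned one. The uncoded counts show how many events occurred, not which. A listing, even if one is produced, is not the summary of frequencies and percentages that the protocol promises.

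On counting, the SAP keeps the worst episode and adds the others, and it spells out neither numerical reading, so the size of the difference is not fixed. That is correct, and the percentages above are illustrations. The rules still differ, and the SAP's subject counts are not tied to worst severity.

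The points on CTM and the relationship scale depend on definitions or CRF wording not available here and are put conditionally. The start of AE recording is a separate protocol inconsistency; protocol 8.2 is the outlier, since the Schedule of Events also begins AE assessment at Baseline. Finally, because the SAP covers three studies, its references to treatment groups could mean the three joint cohorts. That is why the Fisher test is treated below only as clean-up.

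**Conclusion.** The concern holds and should be fixed. SAP 4.4 labels related AEs as treatment-emergent, leaves AEs not judged related without a planned coded table, and uses an episode-counting rule that differs from protocol 9.2.2. The textual conflict depends on no assumption.

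Its numerical effect depends on the events observed and the causality judgements. In the examples, a term at 12% could be reported at any of 0%, 4%, 8% or 12%, and a 36% mild rate becomes 40% or 48%. These rest on 25 treated subjects and invented AE counts. The primary efficacy analysis is unaffected.

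**What to change.** In SAP 4.4:

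1. Define a TEAE as any AE that starts or worsens on or after the study injection.
2. Produce system organ class and preferred term tables for all TEAEs, and separately for those related to product and those related to procedure. Present SAEs by relationship to product and to procedure.
3. In every severity and relationship table, count each subject once at worst severity and strongest relationship, as in protocol 9.2.2, over the Safety Population of SAP 4.5. Put event counts in a separate column.
4. Define CTM and map the SAP's relationship terms to the scale in protocol 8.3.
5. As clean-up, delete the between-group Fisher test, which cannot be computed within this one-arm study.

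In the protocol, reconcile 8.2 with 6.4, 8 and 9.2.2 on when AE recording starts.

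The cost is SAP wording, slightly more table programming and a short protocol clarification. No new data are needed, because all AEs are already to be coded. The visible consequence is that coded AE rates will look higher than under the present definition.

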Not known peptic ulcers with possibility of subsequent perforation and haemorrhage; pancreatitis

Skin and subcutaneous tissue disorders

Very rare: hyperpigmentation or hypopigmentation

Not known: impaired wound healing; thin and fragile skin; petechiae and ecchymoses; facial erythema; increased sweating; purpurea; striae; acneiform eruptions; hives; rash

Musculoskeletal and connective tissue disorders

Very rare: calcinosis; tendon rupture

Not known: loss of muscle mass; osteoporosis; aseptic necrosis of the heads of the humerus and femur; spontaneous fractures; Charcotlike arthropathy

Renal and urinary disorders

Not known: negative nitrogen balance owing to protein catabolism

General disorders and administration site conditions

Common: Local reactions include sterile abscesses, post-injection erythema, pain, swelling and necrosis at the injection site.

Rare: Excess dosage or too-frequent administration of injections into the same site may cause local subcutaneous atrophy, which, due to the properties of the drug will only return to normal after several months.

Adverse events associated with single intra-articular knee injections of Cingal can be found in the Cingal Investigator's Brochure. These events are expected to be similar for ankle injections. In the clinical trial for Cingal in knee OA, adverse events that were related to the injection treatment were:

- injection site pain/swelling
- joint stiffness / swelling / effusion
- arthralgia,
- pain in extremity
- synovitis
- contusion
- subcutaneous nodule
- Baker's cyst

Adverse events not related to the knee for Cingal were:

- headache
- pain in extremity
- upper respiratory tract infection
- back pain

Other risks associated with intra-articular ankle injections, regardless of treatment, include:

- temporary injection site pain, swelling or tenderness
- temporary stiffness of the ankle
- malfunction of the syringe and/or needle

In rare instances, side effects could include:

- an allergic reaction to the fluoroscopic imaging contrast agent. Symptoms could include redness or inflammation at the injection site or inside the ankle joint, hives or itching.
- an allergic reaction to the local anesthetic (lidocaine). Symptoms could include redness or inflammation at the injection site or inside the ankle joint, hives or itching.
- injection site infection
- neurovascular, cartilage, or bone damage resulting from the injection itself

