8.3 Information provided by the clinical investigation site

The principal investigator will provide the following information, at a minimum, for each adverse event (AE) or Adverse Device Effect (ADE):

- Date of the AE or ADE.
- Date Principal Investigator (or authorized designee) became aware of AE or ADE
- Description of AE or ADE, relevant diagnostic findings
- Treatment
- Resolution
- Assessment of:
- 1. severity of the event
 - a. Mild: asymptomatic or mild symptoms; clinical or diagnostic observations only; intervention not indicated.
 - b. Moderate: minimal, local or noninvasive intervention indicated; limiting
 - c. Severe: medically significant but not immediately life-threatening; hospitalization or prolongation of hospitalization indicated; disabling
 - i. Life-threatening: urgent intervention indicated, disabling
 - ii. Fatal: death related to AE

- 2. relationship of the event to the investigational device (related, unlikely related, possible related, probable related or causal relationship)
- 3. relationship of the event to the index procedure (related, unlikely related, possible related, probable related or causal relationship)
- 4. causality
 - a. disease under study
 - b. lack of performance of the investigational device or comparator/worsening of treated condition
 - c. medical history
 - d. concomitant or previous medication
 - e. other (specify)

The principal investigator will supply the sponsor and/or designee, with any additional information related to the safety reporting of a particular event upon request.

The sponsor is responsible for the classification of all adverse events and ongoing safety evaluation of the clinical investigation and shall:

- 1. Review the investigator's assessment of all adverse events and determine and document in writing their seriousness, severity and relationship to the investigational device; in case of disagreement between the sponsor and the principal investigator(s), the sponsor shall communicate both opinions to concerned parties.
- 2. Review all device deficiencies and determine and document in writing whether they could have led to a serious adverse device effect; in case of disagreement between the sponsor and the principal investigator(s), the sponsor shall communicate both opinions to concerned parties.

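### SAP 4.4 classifies TEAEs and SAEs by relationship to CTM alone, although the protocol also collects relationship to the injection procedure and plans to report it

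*SAP*

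**What the plan says.** **Protocol.** Section 8.3 lists what the investigator must assess for each event. Relationship to the investigational device is one item. The next is a separate item on the same scale, the "relationship of the event to the index procedure". Section 9.2.2 plans to summarise subjects with AEs by "system organ class and preferred term, severity, and relationship to investigational product/procedure", and adds that "Serious Adverse Events will also be presented by relationship to investigational product/procedure". The safety endpoint in 6.4 is the incidence, severity and relationship to treatment of all AEs.

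**SAP.** Section 4.4 restricts TEAEs to events that the investigator judges definitely, probably or possibly related to CTM. It summarises those events by class and term, severity, and "relationship to study CTM for each treatment group". For serious events it says: "Serious Adverse Events will also be presented by relationship to the CTM". The procedure is not mentioned as an object of attribution. The final paragraph of 4.4 tabulates subjects and AEs by severity, by relationship without saying to what, and by whether the event was local to the injection site. CTM is not spelled out in the SAP text available or in the protocol's list of abbreviations.

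**The concern.** Every subject who receives Cingal also undergoes the injection, so harm from the injection is part of the harm of the treatment. The procedure in protocol 7.4 can include advancing the needle to the articular surface, contrast or air, peri-articular anaesthetic and aspiration. Protocol 4.2 lists corresponding harms, all described as rare: allergy to contrast or local anaesthetic, injection-site infection, and "neurovascular, cartilage, or bone damage resulting from the injection itself". An investigator could reasonably grade any of these as related to the procedure and unlikely to be related to the product.

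The protocol collects a grade for this case and plans to report it. The SAP says that it gives the detail of the analysis described in the protocol, but its TEAE and SAE rules use only the other grade, and it gives no reason for the change. What is at stake is the relationship component of the safety endpoint, in a study whose stated goal includes safety in a new joint.

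**Working it through.** There is no stated figure to reproduce. The check is a comparison of the texts, followed by tracing an event through the planned outputs.

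**Step 1. Object of the causality grade in each place**

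| Item | Protocol | SAP 4.4 |
|---|---|---|
| Grades collected per event | Device and index procedure, separately (8.3) | Not addressed |
| Which events enter the main summaries | Subjects with AEs (9.2.2) | TEAEs, meaning related to CTM |
| Relationship in those summaries | Product/procedure (9.2.2) | CTM |
| Relationship for SAEs | Product/procedure (9.2.2) | CTM |
| Tabulation of all AEs | Not separately planned | Severity, relationship (object not named), local or non-local |

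**Step 2. Tracing an event through SAP 4.4, reading CTM as the product only**

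- *Related to the product, or to both product and procedure:* the event is a TEAE and appears in the TEAE tables. If serious, it is shown as related. Nothing is lost except the procedure attribution.
- *Related to the procedure only, not serious:* the event fails the TEAE definition, so it is missing from the TEAE tables by class and term, severity and relationship. It remains in the count of subjects with at least one AE, in the number of AEs, and in the local versus non-local split.
- *Related to the procedure only, serious:* as above, and the SAE presentation shows it as not related.

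**Step 3. Which part depends on which sentence**

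The absence from the TEAE tables comes from the TEAE definition. If TEAEs were redefined by timing, a procedure-only event would enter those tables. Two gaps would remain: the TEAE relationship summary and the SAE presentation would each still have no procedure category.

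**Step 4. Size**

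Let n be the number treated, and k the number of subjects whose only related events are procedure-only. Adding the procedure grade raises the proportion of subjects with a related event by k/n. With n = 25 and k = 1, this is 1/25 = 0.04, or 4 percentage points. A procedure-only event in a subject who already has a product-related event adds 0. Two procedure-only events in one subject still add at most 4 points in total. The planned number is 25 in the synopsis, up to 25 in protocol 6.5 and at least 25 in protocol 9.1, so 4 points is the step at exactly 25. The value of k cannot be obtained from the documents.

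**The case against.** A reader might infer that the procedure grade is left out of every planned safety table and that procedure harms would disappear from the report. The documents do not support that. The last paragraph of SAP 4.4 covers all AEs and uses a relationship with no stated object, which could be read to include the procedure. The same paragraph separates local injection-site events from others, so an injection-site infection, and probably local needle damage, would be visible there. The grade itself is still collected. What the TEAE and SAE rules lose is an attribution, not the event. This objection stands and limits the point. It does not remove it, because the TEAE and SAE sentences name CTM explicitly, CTM is the only object of attribution that the section names, and location at the injection site is not a causality grade.

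A reader might also take protocol 9.2.2 to require that an event count as treatment-related if it is related to either product or procedure. It states no such rule. The slash leaves open whether the two grades are shown separately or combined. On either reading, however, the procedure has to appear.

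Two further limits are fair. CTM may be intended to include administration; if so, the mismatch is only one of wording, but the SAP has to say it. And the specific procedure harms in protocol 4.2 are listed as rare, so few events may be affected.

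**Conclusion.** The mismatch is real, and following SAP 4.4 as written would misattribute one kind of event. A procedure-only AE would be left out of the TEAE tables, and a procedure-only SAE would be presented as unrelated, contrary to what protocol 9.2.2 plans. This assumes that CTM means the product without the injection procedure.

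The effect is limited to procedure-only attributions. Their number is unknown, so no actual understatement can be shown in advance. The possible change in the related-subject rate is at most 4 percentage points per newly counted subject if 25 are treated. The primary efficacy analysis is not affected. The change is worth making because it concerns a stated component of the safety endpoint and uses data that are already planned to be collected.

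**What to change.** In SAP 4.4:

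1. Define CTM, and say whether it includes the injection procedure.
2. Present the AE and SAE tables by relationship to product and by relationship to procedure, using the two grades collected under protocol 8.3.
3. State that the relationship in the last paragraph covers both grades.
4. Make sure that the rule for entering the TEAE tables does not exclude events attributed to the procedure alone.

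As a suggestion of this review, not a protocol rule, also report events related to either product or procedure, and keep the product-only column so that the two sources can be told apart.

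The cost is SAP wording and one extra column set, with no new data collection. The downside is that the reported related-event rate may be slightly higher.
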